### **EXCLUSION CRITERIA**

- 1) Currently infected with hepatitis virus and/ or has liver disease
- 2) Current or chronic history of kidney disease or CrCl<60 ml/min
- 3) Continued need for, or use during the 90 days prior to enrollment, of the following medications:
  - a) Systemic immunomodulatory agents
  - b) Supraphysiologic doses of steroids (short course steroids less than 7 days duration, allowable at the discretion of the investigators)
  - c) Chemotherapy or radiation for treatment of malignancy
  - d) Experimental medications, vaccines, or biologicals
- 4) Intent to use HIV antiretroviral pre/post-exposure prophylaxis (PrEP or PEP) during the study, outside of the study procedures
- 5) Current use of hormonal therapy
- 6) Any other clinical condition or prior therapy that, in the opinion of the investigator, would make the patient unsuitable for the study or unable to comply with the study requirements.

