### Study visits

When possible, study activities such as questionnaires will be done remotely due to the ongoing COVID-19 pandemic.

Eligible subjects will be sequentially assigned to study arms: A, B, C & D. Our goal is to have 10 participants complete each arm.

Participants may participate in more than one study arm; however, at least 8 weeks must lapse after completion of one study arm, before entry into another. Participants who participate in more than one arm do not have to repeat the screening visit (visit 1) when starting another arm; they will begin the new arm at visit 2. However, they will be re-consented on the consent form of the new arm prior to any arm-specific study activities being performed.

Participants who are unable to donate hair will not be considered protocol deviations.

The consent process will be conducted in a private exam room at the Hope Clinic or electronically via an online e-consent platform. Copies of the consent form for this project will not be placed in individuals' medical records since this study collects sensitive information such as HIV status and sexual orientation. All participants will be provided a copy of the signed informed consent form (ICF).

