**Visit 19:** Participants will return to the clinic 14 days (+/- 1 day) after their last dose at visit 15. Approximately 24mL of blood will be drawn, urine sample, and a finger stick will be collected, along with an optional hair sample.

**Visit 20:** Participants will return to the clinic 21 (+/- 1 day) days after their last dose at visit 15. Approximately 24mL of blood will be drawn, urine sample, and a finger stick will be collected, along with an optional hair sample.

**Visit 21:** Participants will return to the clinic 28 days (+/- 1 day) after their last dose at visit 15. Approximately 24mL of blood will be drawn, urine sample, and a finger stick will be collected, along with an optional hair sample.

*Biological specimens:*

Hair samples will be taken from those participants who are able to give a hair sample. 50-100 strands of hair will be taken using scissors at the above specified visits.

Biologic specimens collected after the screening visit will be transferred directly to CDC for measurement of study drug levels. Specimens will be labeled with a unique ID that only the Emory study team will be able to link to identifiable information. CDC personnel will not have access to identifiable information.

*Contingency visit:*

Attempts to ensure adherence to the study visits will be made with telephone and/or email reminders to the participant. However, if for example, screening laboratory results are lost or are inconclusive or if a participant has been unable to adhere to study protocol, he may be rescheduled for a future date where the above visit procedures will be performed. These additional visits will be scheduled within the above visit windows.

*Missed Visits:*

In all arms, up to 3 missed visits (~15% of all study visits) are allowed.

*Timing of procedures after dose:*

The procedures conducted after dose, particularly those less than 24 hours after dose, should occur as close to the scheduled time points as possible. Protocol deviations will be filed for visits that occur outside of the target windows identified above only if the visit is conducted more than 3 hours beyond the target window defined above for each arm and visit.

*Phone calls/retention contacts:*

While on study, periodic phone calls, texts, or email reminders will occur between study staff and participants to ensure proper retention and adherence to study protocol.

Statistical Analysis Plan

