## RISKS AND HOW MINIMIZED

### **HIV risk counseling**

Participants that are tested for HIV to ensure eligibility will undergo HIV risk reduction counseling (e.g. increasing condom use, reducing number of partners, addressing substance abuse, etc.) by the study PI or study staff with provision of condoms and lubricant available freely at the Hope Clinic. HIV rapid testing will then be conducted with a CLIA waived product with finger-stick or whole blood from phlebotomy, depending on the test. Any participant who is found to be HIV positive on rapid testing will be referred for confirmatory testing to their local health department, community based organization that provides HIV testing, or provider of their choice. We will also assist any HIV positive participant in accessing healthcare for HIV infection as needed.

Participants will also be educated about HIV pre-exposure prophylaxis during the study by the coordinator and/or study clinician. After completion of the study, all participants who are interested in PrEP for HIV prevention will be linked to community services. A detailed listing of PrEP services available for insured and uninsured clients in Atlanta can be found at [www.prelocator.org](http://www.prelocator.org). [name] is active in PrEP implementation in the Atlanta community and can facilitate these linkages.

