### **Risk of TDF/FTC**

TDF/FTC is a combination anti-HIV medication that contains the drugs tenofovir and emtricitabine. Based on clinical trials previously conducted of TDF/FTC, the drug showed to be well tolerated (see package insert). The most common adverse events reported in clinical trials ( $\geq 5\%$  incidence) included diarrhea, nausea, and headache. Additional adverse reactions occurring in less than 2% of subjects administered TDF/FTC included vomiting, flatulence, dyspepsia, abdominal pain, rash, and depression.

Renal toxicity and bone density loss are rarely reported with chronic use of TDF containing products and are not expected to occur with the regimen prescribed in this protocol. Similarly, lactic acidosis and severe hepatomegaly have rarely been associated with medications in the same class as TDF and FTC.

Use of TDF/FTC can also cause flare-ups in those who have hepatitis B virus. It can cause the Hepatitis B virus to suddenly return in a worse form than before if treatment

was provided (see package insert). For this reason, it is important that participants not participate in the study if they are known to have Hepatitis B.

Acquisition of HIV drug resistance is a theoretic concern for HIV positive people taking intermittent dosing of anti-HIV medication. For this protocol, we will test participants for HIV at study entry and monitor clinically for high-risk behavior or any signs of acute HIV infection at study visits. We will only enroll participants at lower risk for HIV and who report consistent condom use. If high-risk behavior (e.g. unprotected anal intercourse with a man of unknown HIV status) or symptoms of acute HIV infection are reported, and HIV antigen/antibody test will be repeated and the participant will be counseled about the need for any follow-up testing. Clinical signs and symptoms of acute HIV infection that will be queried include: fever, fatigue, malaise, skin rash, swollen glands, oral/genital ulcers, myalgia/arthralgia(3). [name] will review all reports of clinical signs/symptoms to determine appropriate follow-up and linkage to care as necessary. If a diagnosis of acute HIV infection is thought to be possible or determined by repeat HIV testing, the participant will be discontinued from the study.

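### Second-arm entrants restart TDF/FTC with no scheduled HIV or HBsAg retest: the last HIV result is about 12–18 weeks old and the last HBsAg about 13–31, against 1–6 weeks at first entry

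*Combined protocol and SAP*

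**What the plan says.** Under Study visits, a participant may join more than one arm if a minimum of 8 weeks separates completion of one from entry to the next. No maximum is stated there. On screening the text reads "Participants who participate in more than one arm do not have to repeat the screening visit (visit 1) when starting another arm", and then "they will begin the new arm at visit 2". The only step required on re-entry is consent on the new arm's form.

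The arm schedules show what this leaves out:

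- Visit 1 has the HIV, hepatitis B and creatinine tests in every arm.
- Visit 2 is the start of TDF/FTC in every arm and lists none of these tests.
- Arm A has no later scheduled HIV or hepatitis B test.
- Arms B, C and D repeat the HIV test at Visits 6, 10 and 14 and creatinine at Visit 14. They never repeat hepatitis B, and no HIV test is scheduled from Visit 15 to Visit 21.

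First-time entrants move from Visit 1 to Visit 2 in 1–6 weeks.

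**The concern.** Two sentences in Risk of TDF/FTC explain why current results matter before dosing. One is "Acquisition of HIV drug resistance is a theoretic concern for HIV positive people taking intermittent dosing of anti-HIV medication". The other, on hepatitis B flare, is "it is important that participants not participate in the study if they are known to have Hepatitis B". That second precaution depends on knowledge of infection status, and an infection acquired after screening would not be known without a new test.

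The waiver therefore lets a healthy volunteer, who gains no direct benefit from the study, restart intermittent TDF/FTC on old results. The person at risk is one infected since the last test who has no symptoms or reports no risk behavior. This is a participant-safety point. It does not bias the TFV-DP comparisons.

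**Working it through.** The documents give no figure for the age of results at re-entry, so it has to be built from the visit schedule.

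**Inputs stated in the protocol**

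- Visit 1 to Visit 2: 7–42 days (each arm's Visit 1).
- Arm A, Visit 2 to last dose at Visit 3: 2 days.
- Last dose to final visit: 28 ± 1 days, so 27–29 (Visit 9 in Arm A, Visit 21 in Arms B–D).
- Minimum break between arms: 8 weeks, or 56 days.
- Missed visits: "In all arms, up to 3 missed visits (~15% of all study visits) are allowed".

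**Assumptions**

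- Weekly visits in Arms B–D: Visit 14 to Visit 15 takes 0–7 days, Visit 10 to 14 takes 28 days, and Visit 6 to 10 takes 28 days.
- Visit 2 to Visit 15 takes 84–91 days. The 13 weeks is stated for Arm D, and the other two arms share its visit numbering.
- An arm is complete at its final scheduled visit.

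**Formula:** age at re-dosing = (last test to last dose) + (last dose to final visit) + 56 days.

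| Last scheduled result | Sum, days | Age, days | Weeks |
|---|---|---|---|
| After Arm A: HIV and HBsAg, Visit 1 | 7+2+27+56 to 42+2+29+56 | 92–129 | 13.1–18.4 |
| After Arms B–D: HIV, Visit 14 | 0+27+56 to 7+29+56 | 83–92 | 11.9–13.1 |
| Same, Visit 14 missed (HIV from Visit 10) | add 28 | 111–120 | 15.9–17.1 |
| Same, Visits 10 and 14 missed (HIV from Visit 6) | add 56 | 139–148 | 19.9–21.1 |
| After Arms B–D: HBsAg, Visit 1 | 7+84+27+56 to 42+91+29+56 | 174–218 | 24.9–31.1 |
| First entry: both tests | Visit 1 to Visit 2 | 7–42 | 1–6 |

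If the three allowed misses fell exactly on Visits 6, 10 and 14 and none was recovered, the HIV result would also be 174–218 days old. A break longer than 8 weeks adds day for day to every re-entry row.

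**Timeline check.** With 13 weeks of dosing, Arms B–D run 1+13+4 = 18 to 6+13+4 = 23 weeks. That fits the synopsis limit of 24 weeks on study.

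**Comparison with the protocol's own monitoring.** HIV is tested about every 28 days during dosing in Arms B–D. With no visits missed, a re-entrant's HIV result is 83/28 = 3.0 to 129/28 = 4.6 times that interval.

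**When the next test comes.** Arm A is closed (Compensation), so re-entry is now into Arms B–D. The next scheduled HIV test is Visit 6, about 4 weeks in. At 4 pills per 2-1-1 course, that is after 4 × 4 = 16 pills in Arm B, or 2 × 4 = 8 in Arm C (alternate weeks) and Arm D (two weeks on, two off). No HBsAg test follows at any later visit.

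**Creatinine (secondary).** The last result is 92–129 days old after Arm A and 83–92 days old after Arms B–D, or 174–218 days if Visit 14 is missed.

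**The case against.** The waiver is permissive: a site may still test, and no eligibility criterion is removed. Several safeguards remain:

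- The exclusion "Currently infected with hepatitis virus and/ or has liver disease" still applies, as does investigator discretion.
- Clinical monitoring at study visits covers Visit 2 of the new arm, and reported risk behavior or symptoms trigger an HIV test.
- The promise in Risk of TDF/FTC of HIV testing on entering the study might be read to include re-entry.
- A missed test visit can be recovered, since "he may be rescheduled for a future date where the above visit procedures will be performed".

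These narrow the gap without closing it. The hepatitis exclusion rests on history if there is no new test. A triggered HIV test misses infection that is asymptomatic or whose risk goes unreported, and no study visits are scheduled during the break. The promise of testing on entry does not mention re-entry, and the specific waiver points the other way. The contingency visit is optional and confined to the visit windows.

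The synopsis also bears on size. A one-year study loosely limits the break. Two arms from B–D take (7+84+27)+(84+27) = 229 to (42+91+29)+(91+29) = 282 days, leaving about 12–19 weeks for it. If the 24-week limit were cumulative per participant, two such arms could not fit and the 174–218 day HBsAg figure would not arise. That reading would rule out most of the re-entry that Study visits expressly allows, so a per-arm limit is more natural, but the text does not settle it.

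Three further points stand. The difference from first-time entrants is one of degree, since they are not tested at Visit 2 either. The case of three missed HIV tests is an extreme. The 83-day lower bound needs Visits 14 and 15 on the same day.

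**Conclusion.** The concern holds. Followed exactly, the plan re-doses second-arm entrants with no scheduled HIV or HBsAg test. At the minimum break, with no visits missed, the HIV result is about 12–18 weeks old and the HBsAg result about 13–31 weeks old, against 1–6 weeks at first entry. The day counts rest on weekly visit spacing, completion at the final visit, and a 24-week limit that applies per arm. The finding that no test is required rests on none of these.

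The harm cannot be sized. The documents give neither an incidence nor the number of re-entrants, which could be zero. With low-risk, condom-using participants the absolute risk is probably small. This is a worthwhile safety amendment, not a flaw in the trial's primary comparison.

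**What to change.** Amend Study visits so that, before the first dose of any further arm, a re-entrant has:

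1. A negative HIV test at Visit 2, before dosing. The method is already in the protocol: "HIV rapid testing will then be conducted with a CLIA waived product with finger-stick or whole blood from phlebotomy".
2. A negative HBsAg from a sample taken within the previous 6 weeks, which is the first-entry window, reviewed before dosing.

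Creatinine can be run on the same draw to reconfirm the clearance criterion. This is optional: the protocol does not expect renal toxicity with this regimen, and no renal harm is argued here. The rest of the Visit 1 waiver can stay.

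The HIV test adds no visit. HBsAg probably needs one short blood-draw visit, because a sample from the previous arm's final visit would be at least 8 weeks old and so outside the window. At the rates under Compensation that is $20 (contingency visit) to $50 (Arms B–D visit) per re-entrant, plus the assays. Re-consent moves to that visit or is done electronically, which is already allowed. An IRB and consent-form amendment is needed, and part of the waived visit comes back. Arms, dosing, later visits and the primary analysis do not change.

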**ARM B (n=20; arm will close to enrollment once 10 people have completed study visits)**

**Visit 1 (screening):** Eligible MSM will be questioned about their medical history, undergo an HIV test, and a peripheral blood sample for creatinine and hepatitis B testing, as well as testing for baseline levels of study drug. A physical exam may also be completed. Participants will then be asked to return within 1-6 weeks for visit 2.

**Visit 2:** Participants will return to the clinic to receive their first set of study drug for weekly 2-1-1 dosing. The first dose of 2 pills will be taken in clinic, the next dose of 1 pill to be taken 24 hours later at home, and the last dose at home 48 hours from the first dose (24 hours after the second dose). Participants will be instructed to take their 2-1-1 dosing on the same days every week. Participants will be instructed to provide documentation of all other dosing with a time-stamped video or picture.

**Visits 3-14:** Participants will return after finishing their weekly 2-1-1 dose, to do their weekly convenience sampling. Approximately 24 mL of blood will be drawn, urine sample, and a finger stick will be collected. An HIV test will be completed at visits 6, 10 and 14 (once per month) along with hair samples. Urine and rectal STI screenings will be conducted at visit 10. An additional creatinine test will be done at visit 14. Participants will be provided with their medication at visits 5, 8, and 11.

**Visit 15:** Participants will return to the clinic to take their final dose of study drug in clinic. After the dose is taken, approximately 24mL of blood will be drawn, urine sample, and a finger stick will be collected.

**Visit 16:** Participants will return to the clinic 24 (+/- 2 hrs) hours after their last dose at Visit 15. Approximately 24mL of blood will be drawn, urine sample, and a finger stick will be collected.

**Visit 17:** Participants will return to the clinic 2-5 days after their last dose at Visit 15. Approximately 24mL of blood will be drawn, urine sample, and a finger stick will be collected.

**Visit 18:** Participants will return to the clinic 7 (+/- 1 day) days after their last dose at Visit 15. Approximately 24mL of blood will be drawn, urine sample, and a finger stick will be collected.

**Visit 19:** Participants will return to the clinic 14 days (+/- 1 day) after their last dose at Visit 15. Approximately 24mL of blood will be drawn, urine sample, and a finger stick will be collected.

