**Visit 20:** Participants will return to the clinic 21 (+/- 1 day) days after their last dose at Visit 15. Approximately 24mL of blood will be drawn, urine sample, and a finger stick will be collected.

**Visit 21:** Participants will return to the clinic 28 days (+/- 1 day) after their last dose at Visit 15. Approximately 24mL of blood will be drawn, urine sample, and a finger stick will be collected, along with a hair sample.

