**ARM C (n=20; arm will close to enrollment once 10 people have completed study visits)**

**Visit 1 (screening):** Eligible MSM will provide informed consent, be questioned about their medical history, undergo a physical exam (conducted by a study clinician), a rapid HIV test, and a peripheral blood sample for a complete blood count, creatinine, coagulation test, and hepatitis B testing. Participants will then be asked to return within 1-6 weeks for visit 2.

**Visit 2:** Participants will return to the clinic to receive their first set of study drug for alternate week 2-1-1 dosing.. Participants will be instructed to provide documentation of all dosing with a time-stamped video or picture and provided with a calendar detailing when they should take the study drug. Participants will take the first 2 pills of their 2-1-1 dosing before leaving this visit.

**Visit 3-14:** Participants will return to do their weekly convenience sampling. Approximately 24 mL of blood will be drawn, urine sample, and a finger stick will be collected. A rapid HIV test will be completed at visits 6, 10 and 14 (once per month) along with optional hair samples. Participants will have urine and rectal STI testing at visit 10. An additional creatinine test will be done at visit 14. Participants will be provided with their medication at visits 5, 8, and 11.

**Visit 15:** Participants will return to the clinic to take their final dose of study drug in clinic. After the dose is taken, approximately 24mL of blood will be drawn, urine sample, and a finger stick will be collected.

**Visit 16:** Participants will return to the clinic 24 (+/- 2 hrs) hours after their last dose at visit 15. Approximately 24mL of blood will be drawn, urine sample, and a finger stick will be collected.

**Visit 17:** Participants will return to the clinic 2-5 days after their last dose at Visit 15. Approximately 24mL of blood will be drawn, urine sample, and a finger stick will be collected.

**Visit 18:** Participants will return to the clinic 7 (+/- 1 day) days after their last dose at visit 15. Approximately 24mL of blood will be drawn, urine sample, and a finger stick will be collected, along with an optional hair sample.

**Visit 19:** Participants will return to the clinic 14 days (+/- 1 day) after their last dose at visit 15. Approximately 24mL of blood will be drawn, urine sample, and a finger stick will be collected, along with an optional hair sample.

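### A participant entering a second arm may skip the visit that holds the HIV test, so no scheduled test precedes the first two pills of the new arm

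*Combined protocol and SAP*

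**What the plan says.** The Study visits section allows participation in more than one arm, provided that "at least 8 weeks must lapse after completion of one study arm, before entry into another". Those who do so "do not have to repeat the screening visit (visit 1) when starting another arm; they will begin the new arm at visit 2". The only other step it requires is consent on the new arm's form.

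Visit 1 is where each arm places its entry HIV test. For a first-time entrant the dosing visit follows closely: "Participants will then be asked to return within 1-6 weeks for visit 2" (Arm B, with the same window in the other arms).

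Dosing starts at Visit 2. Arm B says "The first dose of 2 pills will be taken in clinic", and Arm C says "Participants will take the first 2 pills of their 2-1-1 dosing before leaving this visit". Arms A and D also give two pills at that visit. No arm lists an HIV test there.

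Later scheduled tests differ by arm. In Arm B, "An HIV test will be completed at visits 6, 10 and 14 (once per month) along with hair samples". In Arm C, "A rapid HIV test will be completed at visits 6, 10 and 14 (once per month) along with optional hair samples", and Arm D has the same schedule. Arm A lists none after Visit 1. Follow-up in Arms B-D ends at Visit 21: "Participants will return to the clinic 28 days (+/- 1 day) after their last dose at Visit 15".

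Under Risk of TDF/FTC, the protocol names drug resistance as a theoretical concern when HIV-positive people are dosed intermittently. Its stated safeguards are an HIV test on entering the study, clinical monitoring at visits, and a repeat test if risk behaviour or symptoms of acute infection are reported.

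**The concern.** The protocol relies on a recent negative test before it starts intermittent TDF/FTC. On re-entry it waives the visit that contains that test and puts nothing in its place, although the participant has by then gone longer without a scheduled test than any first-time entrant within the screening window. Followed as written, the rule permits a 2-1-1 course to begin in a man with an undiagnosed infection. That is the situation which the risk section describes as the resistance concern. What is at stake is participant safety, not the TFV-DP comparison.

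**Working it through.** The documents give no test-to-dose interval for re-entrants, so there is no figure to reproduce. The rest is calendar arithmetic.

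**Inputs**
- Screening to Visit 2: 1 to 6 weeks (arm descriptions).
- Gap between arms: at least 8 weeks = 56 days (Study visits).
- Arms B-D: last scheduled test at Visit 14; Visit 15 to Visit 21 is 28 ± 1 days.
- Arm A: only test at Visit 1; Visit 2 to last dose is 2 days; last dose to Visit 9 is 28 ± 1 days.
- Up to 3 missed visits allowed (Missed Visits).
- Visit 14 to Visit 15: not stated. I assume at least 1 day. On a weekly calendar Visit 14 falls in week 12 (days 77 to 84 from Visit 2) and the last pill of the week-13 course on day 86, a gap of 2 to 9 days.

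**First-time entrant, test to first dose**
1 × 7 = 7 days to 6 × 7 = 42 days.

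**Re-entry with completion at the final visit**
- From Arms B-D, floor: 1 + 27 + 56 = 84 days.
- From Arms B-D, weekly calendar: 2 + 27 + 56 = 85 to 9 + 29 + 56 = 94 days.
- From Arm A: 7 + 2 + 27 + 56 = 92 days at the least. If screening was 6 weeks before Visit 2, the minimum is up to 42 + 2 + 29 + 56 = 129 days.

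**Re-entry with missed visits**
- Arms B-D, Visits 19-21 missed and completion counted from Visit 18 (7 ± 1 days after the last dose): 1 + 6 + 56 = 63 days.
- Arm A, Visits 7-9 missed and completion counted from Visit 6 (7 ± 1 days): 7 + 2 + 6 + 56 = 71 days.
- Arms B-D, Visit 14 itself missed, so that the last test is at Visit 10: about 28 + 7 + 28 + 56 = 119 days.

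Every route exceeds 42 days. All of these are minimum waits, because the 8-week rule sets no upper limit of its own.

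**Exposure before the next scheduled test**
In Arms B-D the next test is at Visit 6, about 28 days after Visit 2. At 4 pills per course, that is 4 × 4 = 16 pills in Arm B, 2 × 4 = 8 in Arm C (weeks 1 and 3) and 2 × 4 = 8 in Arm D (weeks 1 and 2).

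**Likely yield**
The number of re-entrants is not given and may be zero. Per 10 re-entrants from Arms B-D, the untested time at the minimum wait is 10 × 63 / 365.25 = 1.72 to 10 × 94 / 365.25 = 2.57 person-years. At an assumed incidence of 0.5 to 3 per 100 person-years (not in the documents), this gives 1.72 × 0.005 = 0.01 to 2.57 × 0.03 = 0.08 infections. Those caught through reported risk or symptoms have not been removed.

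**The case against.** The waiver is permissive. It excuses the screening visit but not eligibility: the inclusion criteria still require an HIV-negative person, and the risk section promises a test on entering the study. The Design summary caps time on study at 24 weeks. If that cap applies per participant, re-entry is impossible, since Arm A (about 4 weeks from Visit 2), the 8-week gap and a further arm (about 13 + 4 = 17 weeks) total about 29 weeks. If it applies per arm, each arm is a fresh period on study, and the entry test could be held to recur. The arm-specific consent forms are not in the text reviewed and might list a test.

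This part stands: a site could reasonably test, and nothing forbids it. It does not settle the matter. The per-participant reading would void the re-entry rule. The per-arm reading makes a repeat test possible without requiring it. A site that follows the Study visits text can dose without one.

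Two further objections also stand. Visit 2 is a study visit, so monitoring for risk behaviour and symptoms applies there; what remains is infection with neither reported, in a population selected for low risk and consistent condom use. And 42 days is a scheduling window that the protocol never presents as the period for which an HIV test stays valid. It serves here only as a description of what first-time entrants get.

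Skipping Visit 1 also skips the hepatitis B and creatinine tests. This point is confined to HIV, the status that the protocol ties to the hazard of intermittent dosing and retests monthly in Arms B-D.

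**Conclusion.** The concern holds and is minor. No scheduled HIV test precedes the first dose on re-entry. The last one is at least about 84 days old after Arms B-D and 92 days after Arm A if completion means the final visit. It is about 63 days old on the shortest Arm B-D route, with the last three visits missed. The 84-day figure assumes at least one day between Visits 14 and 15. Arm A is closed, but its completers may still enter another arm.

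A reader might infer more than the documents support:
- *That 84 days is a hard floor, or that a 42-day limit is breached.* The missed-visit allowance lowers the floor, and there is no such limit.
- *That infected men are likely to be dosed.* The expected number is a small fraction of one per 10 re-entrants, before existing safeguards are counted.
- *That the primary result is at risk.* The TFV-DP comparisons do not depend on this test.
- *That an exit test at Visit 21 is needed.* With Visit 21 attended, re-dosing comes at least 56 days after it, so a test there could not replace one at Visit 2.

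**What to change.** Add one sentence to the Study visits section, after the re-entry rule: *A participant entering another arm must have a negative rapid HIV test at Visit 2 before the first dose.* The test-to-dose interval on re-entry then falls to the same visit.

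The HIV risk counseling section already describes a suitable CLIA-waived rapid product and a referral route for reactive results. The cost is a one-line amendment and, per re-entry, one kit, one extra finger stick (Visit 2 lists no sampling) and a few minutes of staff time. The downside is an occasional false-reactive result, which would delay dosing until confirmatory testing is resolved. No dose, dosing schedule or analysis changes.
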